4.4. Pharmacokinetics Analysis Set

The Pharmacokinetics analysis set for subjects in Part A and Part B will include all subjects who received at least one administration of test material (izokibep or placebo) and have at least 1 quantifiable PK concentration.

4.5. ADA Analysis Set

The ADA analysis set for subjects in Part A and Part B will include all subjects who received at least 1 administration of test material (izokibep or placebo) and have both baseline ADA and at least 1 post-dose ADA measurement.

5. Data Handling

5.1. Time Points and Visit Windows

5.1.1. General Definitions

All assessment days will be related to the first day of the first dose of the study drug.

Day 1 is defined as the date of the first dose of the study drug. Relative days after Day 1 are calculated as (assessment date – Day 1 date) + 1. Relative days prior to Day 1 are calculated as (assessment date – Day 1 date). The day prior to Day 1 is Day -1. There is no Day 0.

The date of the first dose of study drug for each subject will be taken from the Study Drug Administration CRF page. If the date in this CRF page is missing, alternatively the date of enrollment/randomization will be used.

The date of the last dose of study drug for each subject will be taken from the Study Drug Administration form, with the last study drug administration date from any visit used as the date of last study drug.

5.1.2. Screening Period

For all subjects, the screening period starts when the subject signs and dates the informed consent form (ICF) and ends when the subject is enrolled/randomized, or screen failed. The screening period is up to 28 days. Certain initial screening period procedures may be repeated during the original initial screening period. This is not considered "rescreening," which may occur in this study. These procedures include laboratory assessments due to value(s) out of range due to potential sampling error or that could be within range with repeat sampling.

The baseline value for a variable is therefore defined as the last non-missing value collected before enrollment/randomization.

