6.3.3.2. Treatment Assignment Part B

Part B is a double-blind, randomized investigation. Subjects will be randomized to the study drug (QW or Q2W) on Day 1 by IXRS. Randomization will be based on a schedule generated by the sponsor or sponsor designee before the start of the study and will be centrally executed using the IXRS. The subject, site personnel, and sponsor/Contract Research Organization (CRO) study personnel and designees will be blinded to the randomization treatment group assignment (ie, izokibep or placebo) but not to the dosing schedule (QW or Q2W). The randomization dates are to be documented in the subject's medical record.

Randomization will be stratified by any prior biologic and/or JAK inhibitor use for HS (Yes/No) as well as by Hurley Stage (II or III).

Izokibep and matching placebo will be visually indistinguishable to prevent unblinding during preparation or administration of study material.

Subjects assigned to receive placebo will be randomized in a 1:1 ratio to receive placebo administered QW or Q2W. This will allow for blinding of test material, while the treatment schedule (QW or Q2W) will not be blinded from the subject or site personnel, and also will not be blinded from sponsor staff or designee who have access to administration logs.

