7.3. Lost to Follow-up

A subject will be considered lost to follow-up if he/she repeatedly fails to return for scheduled visits and is unable to be contacted by the study site.

The following actions must be taken if a subject fails to return to the clinic for a required study visit:

- The site must attempt to contact the subject and reschedule the missed visit as soon as possible, counsel the subject on the importance of maintaining the assigned visit schedule and ascertain whether the subject wishes to and/or should continue in the study.
- Before a subject is deemed lost to follow-up, the investigator or designee must make every effort to regain contact with the subject (where possible, 3 telephone calls, and if necessary, a certified letter to the subject's last known mailing address or local equivalent methods). These contact attempts should be documented in the subject's medical record.
- Should the subject continue to be unreachable, he/she will be considered to have withdrawn from the study.

8. Study Assessments and Procedures

- Informed consent must be obtained before any study-related procedures are performed. In regions where the legal age of consent is older than 18 years, informed consent must be obtained from and signed by the subject.
- Study procedures and their timing are summarized in the SoA (Section 1.3). Protocol waivers or exemptions are not allowed.
- Day 1 corresponds to the date of the first dose of study drug.
- Visit/dosing windows of ±3 days on either side of the scheduled visits/dosing are permitted; however, the investigator should try to keep the subjects on the original visit/dosing schedule. The window of ± 3 days is relative to Day 1 and applicable for all subsequent visits/dosing. For QW dosing, the time between doses should be no less than 4 days and no more than 10 days. For Q2W dosing, the time between doses should be no less than 11 days and no more than 17 days.
- All assessments are to be completed before study drug administration, unless otherwise specified. It is recommended that patient-reported outcome assessments be completed first.
- Immediate safety concerns should be discussed with the sponsor immediately upon occurrence or awareness to determine if the subject should continue or discontinue study drug.
- Adherence to the study design requirements, including those specified in the SoA, is essential and required for study conduct.

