9.3. Statistical Analyses

9.3.1. General Considerations

Data from Part A and Part B will be summarized separately.

All data collected will be summarized by planned timepoint without imputation. Continuous data will be summarized with count, mean, median, standard deviation, minimum, and maximum. Change from baseline will additionally include standard error. Categorical data will be summarized with count and percent. Time to event data will be summarized with product-limit estimators of median and quartiles. Placebo subjects assigned to receive doses QW or Q2W will be summarized both separately and combined, with hypotheses tested using both placebo dosing frequencies combined.

All hypothesis tests will use only data from Part B and will be reported with two-sided p-values. Comparison of QW dosing to placebo will use only subjects assigned to receive izokibep QW or

placebo; comparison of Q2W dosing to placebo will use only subjects assigned to receive izokibep Q2W or placebo. All CIs will be two-sided with nominal 95% coverage.

Data will be summarized by part and planned timepoint, using data collected at the visit. Study day will be calculated as post-baseline date minus randomization date, plus 1 (except that study day for pre-randomization dates will not include the plus 1). Day range windows will not be applied for summaries (but may be applied for protocol deviations). Baseline values will be the last value collected before randomization and change from baseline will be calculated as post-baseline value minus baseline value.

For testing purposes, subjects randomly assigned to placebo QW and placebo Q2W will be grouped together into a single placebo group for comparison to each dosing regimen of izokibep. This assumes that dosing with placebo QW or Q2W does not affect efficacy, an assumption which will be explored with simple summary statistics. Stratified tests will use the 4 strata from the randomization process. If a subject is incorrectly classified during the randomization process, the analysis will use the correct classification, not the classification used during randomization.

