2.4. Primary Efficacy Variable

The primary efficacy variable for Part A and Part B is HiSCR75, the proportion of subjects who achieve at least a 75% reduction from baseline in the total AN count, with no increase from baseline in abscess or draining fistula count. The primary timepoint for analysis is Week 12 for Part A and Week 16 for Part B.

HiSCR50/75/90/100 is defined as meeting all three criteria below:

- (AN count at baseline AN count at current visit) / AN count at baseline \times 100% \geq 50/75/90/100%
- Abscess count at baseline \geq abscess count at the current visit
- Draining fistula count at baseline \geq draining fistula count at the current visit

where AN count is abscess count + inflammatory nodule count, and abscess count and fistula count are summed across all regions and are inclusive of all abscesses, inflammatory nodules and fistula that have previously undergone localized surgical or medical intervention and are no longer present. The baseline value for lesion count (including draining fistula count) and Hurley stage is the latest value on or before the randomization day (Day 1).

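### Baseline is cut off at randomisation on Day 1, so a protocol-compliant Day 1 value taken after the IXRS call but before dosing is not baseline; for ADA and four other measures nothing can replace it

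*SAP*

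**What the plan says.** **Baseline rule.** SAP 5.1.2: "The baseline value for a variable is therefore defined as the last non-missing value collected before enrollment/randomization". Protocol 9.3.1: "Baseline values will be the last value collected before randomization". SAP 5.1.2 also says that the screening period "ends when the subject is enrolled/randomized, or screen failed".

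**When randomisation happens.** Protocol 6.3.3.2, for Part B: "Subjects will be randomized to the study drug (QW or Q2W) on Day 1 by IXRS". Part A subjects are also assigned by IXRS on Day 1 (Protocol 6.3.3.1). For the record of the event, Protocol 6.3.3.2 asks for a date: "The randomization dates are to be documented in the subject's medical record".

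**When Day 1 assessments happen.** Protocol Section 8: "All assessments are to be completed before study drug administration, unless otherwise specified". Footnote m of the Schedule of Activities sets the same limit for PK and ADA samples.

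**How Day 1 data are allocated.** SAP 5.1.3 uses the first dose as the divider. A Day 1 value goes to the screening period if its recorded time is earlier than the dose time. If no collection time was recorded, it still goes there where the protocol or CRF calls for Day 1 assessments before dosing.

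**Who is in the ADA set.** SAP 4.5 takes treated subjects who "have both baseline ADA and at least 1 post-dose ADA measurement".

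**Variables with their own rule.** SAP 2.4 lets the randomisation day itself supply the baseline lesion counts and Hurley stage. SAP 2.5 defines baseline worst skin pain from a 7-day window that ends on the first dosing day.

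**The concern.** The baseline definition and the assessment schedule use different events on the same day. Baseline closes at the IXRS call; the permitted time for assessments closes at the injection. A site may confirm eligibility, call IXRS, draw blood and then dose without deviating from the protocol. The rule in SAP 5.1.2 then rejects that blood sample as baseline, while SAP 5.1.3 files it under screening.

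Two things are at stake. For measures first collected on Day 1, the subject has no baseline at all. The most important is ADA, because immunogenicity is a secondary objective in both parts and a baseline ADA is a condition of entry to its analysis set. For measures also collected at screening, an older value is used although a fresher pre-treatment one exists. In both cases the result depends on the order of work at a site, which has no scientific meaning, and two programmers could derive different baselines from the same record.

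**Working it through.** No figure in the plan bears on this, so the check sets the rules side by side.

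**Step 1. One Day 1 value, taken after the IXRS call and before dosing.**

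| Rule | Cut-off | Status of the value |
|---|---|---|
| Protocol Section 8; Schedule footnote m | first dose | compliant |
| Protocol 9.3.1; SAP 5.1.2 | randomisation or enrolment | not baseline |
| SAP 5.1.3 | first dose | screening-period data |
| SAP 5.1.4, Table 1 | Day 1 | baseline time point |

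SAP 5.1.2 ends screening at randomisation and SAP 5.1.3 extends it to the first dose, so the SAP contradicts itself. Table 1 is formally a mapping for early-termination visits, but it shows which visit the authors regarded as baseline.

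**Step 2. Which measures lack a fallback.** In the Schedule of Activities, ADA, HS-PGA, erythema, EQ-5D and HbA1c are marked on Day 1 and not at screening. Nothing in the protocol ties any of them to a time before the IXRS call. HS-PGA and erythema may well be scored at the eligibility lesion count, but that order is not required. For EQ-5D, Section 8 only recommends completing patient-reported outcomes first.

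Consequences where baseline is missing:
- ADA: the subject fails the condition in SAP 4.5.
- EQ-5D: change to Week 16 is undefined (SAP 6.6.5).
- HS-PGA: the subject has no starting category in the shift table (SAP 6.6.5).
- Erythema: the baseline summary has a gap (SAP 6.4.2); later scores are only listed.
- HbA1c: later values have no reference.

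**Step 3. Which measures fall back.** Hematology and chemistry, CRP, vital signs and HADS are marked at both screening and Day 1. Screening may be up to 28 days before Day 1, so baseline could be that old. SAP 6.7.3 and 6.7.4 expressly apply the 5.1.2 definition to laboratory and vital-sign changes. HADS is less exposed because of the recommendation in Section 8.

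**Step 4. Which measures are not affected.**
- Lesion counts and Hurley stage: inclusion criteria 4 and 5 and exclusion criterion 1 require them on Day 1 before randomisation, so both documents lead to the same baseline. This covers HiSCR75, the other HiSCR levels, flare and AN count.
- Skin pain: SAP 2.5 has its own window.
- DLQI and SF-12: Protocol 8.1.6 and 8.1.7 ask for them ahead of any clinic assessment. The Day 1 lesion count is such an assessment and itself precedes randomisation, so a site following these instructions collects both in time.
- HS-PGIC asks about change since the last visit (Protocol 8.1.9). PK is summarised by visit, and its analysis set needs no baseline (SAP 4.4, 6.8).

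**Step 5. Size.** Subjects affected = subjects in the part × share whose value fell between IXRS and dosing. The first factor is about 170 in Part B and 20 to 30 in Part A. The second is not given, could lie anywhere from none to all, and may differ by measure. No count can be derived.

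**The case against.** The strongest reply is that the intent is plain. The word introducing the baseline sentence in SAP 5.1.2 derives baseline from the screening period, and SAP 5.1.3 puts pre-dose Day 1 data there. SAP 2.6 lists a baseline PK trough, and SAP 6.4.2 plans baseline summaries of HS-PGA, erythema, DLQI, EQ-5D and SF-12, none of which has a screening assessment. On this view a sensible programmer will use pre-dose Day 1 values, and only a clarification is needed.

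Much of this stands as evidence of intent. It does not cure the text: SAP 5.1.3 allocates data to periods and does not amend a definition that names randomisation, and Protocol 9.3.1 names it again. If the intent is first dose, the written rule is wrong.

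The reply does defeat a stronger reading. Because only the randomisation date must be documented, a reader might infer that the rule works by date, that no Day 1 value qualifies, and that every subject loses baseline and the ADA set is empty. That application would void the planned baseline outputs in SAP 2.6 and 6.4.2 and contradict the Day 1 entry in Table 1, so the documents do not support it.

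It is also fair that ADA results are descriptive, as counts and percentages by visit with no test (SAP 6.9). The harm is to the denominator and to consistency, not to a hypothesis.

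**Conclusion.** The point holds as a conflict between stated rules. A compliant value taken between the IXRS call and the first dose is excluded as baseline by SAP 5.1.2 and Protocol 9.3.1. The consequence is a missing baseline for ADA, HS-PGA, erythema, EQ-5D and HbA1c, loss from the ADA Analysis Set, and an older baseline for laboratory values, CRP, vital signs and possibly HADS. The change should be made, but it does not threaten the trial's main conclusions.

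A reader might infer that the primary analysis or DLQI is at risk; Step 4 of the working shows why not.

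The conclusion assumes that some sites carry out Day 1 procedures after the IXRS call, which the protocol allows but the documents do not quantify. It also assumes that the ADA summaries use the set in SAP 4.5, since SAP 6.9 names no population.

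**What to change.** In SAP 5.1.2, for every variable without its own rule, define baseline as the last non-missing value collected before the first dose of study drug, stating that pre-dose Day 1 values count. For subjects enrolled or randomised but never dosed, use the last value on or before the enrolment or randomisation date; SAP 5.1.1 already substitutes that date when the first-dose date is missing. Make the end of the screening period agree with SAP 5.1.3. Sections 4.5, 6.7.3 and 6.7.4 then follow without separate edits, and the rules in SAP 2.4 and 2.5 can stay.

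Make the same change in Protocol 9.3.1 at the next amendment. Amendments go to the IRB/IEC (Protocol 10.1.1), so this sentence need not prompt one; until then the SAP should note the difference.

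The cost is a sentence or two and no new data. There is one small downside. After assignment, the dosing frequency is known to subject and site, though active versus placebo is not (Protocol 6.3.3.2). A subjective measure taken between IXRS and dosing, such as EQ-5D, HADS or HS-PGA, could be slightly influenced by that knowledge. ADA and laboratory results should not be.

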5.1.3. Treatment Period

Data collected on Day 1 will be assigned to the Treatment Period unless the time (HH:MM) of data collection and time (HH:MM) of the first dose of study drug are both recorded and the data collection time is before the time of the first dose of study drug. In this case, the assessment will be assigned to the screening period. If the time (HH:MM) of data collection is not recorded but the protocol and/or CRF includes an instruction to the effect that all Day 1 assessments are to be performed prior to the first dose of study drug, the data collected at Day 1 will be assigned to the screening period. However, adverse events and concomitant medications starting on Day 1, will be assigned to the Treatment Period, unless the time (HH:MM) demonstrates otherwise.

The Treatment Period is defined as the period from the date/time of the first dose of study drug to Week 32 (four weeks after the last dose) or early termination/end of treatment visit (within two weeks from the last dose).

Treatment will be divided into two periods, Period 1 and Period 2. In Part B, Period 1 will start at the first dose of study drug and end at Week 16 when Week 16 assessments are completed and before administration of study drug. Period 2 will start at the time of first administration of study drug at or after Week 16 and end at Week 32 or early termination/end of treatment visit.

5.1.4. Visit Windows

All data will be analyzed using the nominal study visit as defined in the SoA in the protocol and CRF.

In the event that a subject discontinues the study early, the subject will have an early termination visit which includes efficacy assessments. If the early termination visit occurs in a timeframe that corresponds to a scheduled efficacy assessment (week 4, 8, 12, 16, 24 or 32), and if the subject does not have an actual visit at or after the corresponding scheduled efficacy assessment, the following day ranges will be used to map the early termination visit to a scheduled efficacy summaries at that timepoint.

Time Point	Time Point Window ^a	
Baseline	Day 1	
Week 4	Days 21 to 42	
Week 8	Days 43 to 70	
Week 12	Days 71 to 98	
Week 16	Days 99 to 112	
Week 24	Days 113 to 196	
Week 32	Days 197 or later	

 Table 1 Definition of Time Point Windows for Analyses

^a relative to the date of first dose of study drug during the Treatment Period/date of Baseline Visit (Day 1)

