3.1.4. Handling of Intercurrent Events to Reflect the Clinical Question of Interest

The treatment policy strategy approach for the estimand will be used in general, so subjects will be included using observed data at Week 16 regardless of treatment compliance, use of rescue medications except as noted below, or any other protocol deviation. Subjects with missing HiSCR75 assessments at Week 16 will be imputed as non-responders (non-response imputation or NRI). A composite strategy will be used for intercurrent events of receiving oral antibiotic therapy that could affect HS: a list of all subjects who received oral antibiotic therapy that results in such imputation will be finalized after review of all oral antibiotic therapy received by any subject and before unblinding of the study, and will include any subject who initiated a new regimen of tetracycline, clindamycin, and possibly other products, and any subject who was on a stable dose of minocycline or doxycycline at randomization but received a higher dose during the study. The endpoint for such subjects will be imputed using NRI.

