To assess the pattern of initial onset, AESIs and ISRs will also be presented by Kaplan-Meier plot. This summary will be done for the full study period and, separately, only for Period 2. For the Period 2 summary, the day of onset will be calculated with respect to the Week 16 date of dosing (Date of AE - Date of Week 16 dose + 1).

Separate Kaplan Meier (KM) plots will be created for the study duration and Period 2 for time to:

- First onset of an event in each AESI category
 - If an AESI category has < 3 events in a treatment arm, then this analysis will not be done.
 - Subjects who do not experience an event will be censored at their date of last contact.
- First ISR
 - Subjects who do not experience an event will be censored at the date of their last injection.

The date/time of onset of the first instance of the event of interest (AESIs or ISRs) will be used as the date/time of the event in the analysis.

The product limit estimator will be presented by treatment group for Week 4 (Day 28), Week 8 (Day 56), Week 12 (Day 84), Week 16 (Day 112), Week 20 (Day 140), Week 24 (Day 168), Week 28 (Day 196), and Week 32 (Day 224) for each AESI category and for ISRs.

Incidence of ISRs will be summarized for the whole study period by treatment group, and injection visit week (Day 1, Week 1, Week 2, etc). If a subject didn't have an injection at the visit week, they will not be counted in the denominator for the incidence calculation.

A similar presentation of ISRs by treatment group and injection visit week will also be done, but the cumulative number of ISRs up to the injection visit week will be summarized at the visit week. This summary will be done for the full study period as well as by treatment period.

An overall summary of ISRs will be produced by treatment group, Period 1, Period 2, and for the full 32 week treatment period. The summary will include the number of subjects with:

- ISRs leading to discontinuation
- ISR at each maximum intensity/severity
- Related ISRs
- Serious ISRs
- Serious related ISRs

An ISR is considered to correspond to a particular visit week if it occurs on or after the indicated injection visit date/time, and prior to the next inject visit date/time. If no subsequent injection visit date/time is available, then the ISR will correspond to the closest injection visit date occurring prior to it.

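### SAP Table 1 ends the Week 16 early-termination window at Day 112, one day before Week 16 falls under the SAP's own day count (Day 113); a minor correction that may affect few or no subjects

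*SAP*

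**What the plan says.** **Day count.** SAP 5.1.1 states that "Day 1 is defined as the date of the first dose of the study drug". It adds 1 to later date differences and says: "The day prior to Day 1 is Day -1. There is no Day 0". Protocol 9.3.1 also adds 1, but counts from randomization: "Study day will be calculated as post-baseline date minus randomization date, plus 1". The two rules agree when randomization and first dose are both on Day 1.

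**Windows.** SAP 5.1.4 uses the nominal visit for all data, with one exception. An early-termination visit is placed by day range when it falls in the timeframe of a scheduled efficacy assessment and the subject has no actual visit at or after that assessment: "the following day ranges will be used to map the early termination visit to a scheduled efficacy summaries at that timepoint". Table 1 counts from the same Day 1. Its windows for Weeks 4, 8, 12, 16 and 24 end on Days 42, 70, 98, 112 and 196. The first opens on Day 21, each later one opens the day after the one before it closes, and the Week 32 window has no upper limit. The Week 16 window is therefore Days 99 to 112, and the Week 24 window opens on Day 113.

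**End of Period 1.** SAP 5.1.3 has Period 1 "end at Week 16 when Week 16 assessments are completed and before administration of study drug".

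**Another day label.** The Kaplan-Meier reporting days in SAP 6.7.2 use weeks times seven: "Week 12 (Day 84), Week 16 (Day 112), Week 20 (Day 140").

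**Protocol on windows.** Protocol 9.3.1 says: "Day range windows will not be applied for summaries".

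**The concern.** Week 16 is the primary timepoint in Part B. The primary estimand in SAP 3.1.4 says that "subjects will be included using observed data at Week 16 regardless of treatment compliance". If the window stops one day short, a lesion count taken exactly on the Week 16 target day can be filed under Week 24. Week 16 is then missing, and SAP 5.2.1 sets HiSCR75 to non-response. SAP 6.6.3 carries the same approach to HiSCR50, HiSCR90 and HiSCR100. SAP 6.6.3.2 does the same for an AN count of 0, 1 or 2 in subjects with baseline Hurley Stage II.

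The supplementary analyses in SAP 6.6.2 do not repair this. The tipping-point analysis assigns such a subject a random response, and the multiple imputation draws a Week 16 value from a placebo-based model. Both treat Week 16 as missing, so neither restores the count that was observed.

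**Working it through.** **Inputs.** Day rule: SAP 5.1.1. Windows: SAP 5.1.4, Table 1. Visits scheduled from Day 1: SAP 2.1. Permitted visit window of ±3 days: protocol 1.3, footnote a. Early-termination visit within 2 weeks of the last dose, with Week 32 procedures (which include the lesion count): protocol 1.3, footnote p. Arm sizes: protocol 1.1 and 9.5.

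**Step 1. Reproduce the plan's limit.** 7 × 16 = 112. This matches Table 1's upper limit and the label in SAP 6.7.2, but it leaves out the +1 that SAP 5.1.1 requires.

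**Step 2. Target days under SAP 5.1.1.** Week w falls on Day 7w + 1.

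| Week | Target day | Table 1 window | Target inside? | Days from target to window end |
|---|---|---|---|---|
| 4 | 29 | 21–42 | yes | 13 |
| 8 | 57 | 43–70 | yes | 13 |
| 12 | 85 | 71–98 | yes | 13 |
| 16 | 113 | 99–112 | **no** | −1 |
| 24 | 169 | 113–196 | yes | 27 |
| 32 | 225 | 197 onward | yes | open |

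**Step 3. How the other boundaries were set.** Midpoints of adjacent targets are:

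- (29 + 57)/2 = 43
- (57 + 85)/2 = 71
- (85 + 113)/2 = 99
- (113 + 169)/2 = 141
- (169 + 225)/2 = 197

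Table 1's windows start at 43, 71, 99, 113 and 197. Only the Week 24 start departs from the midpoint (113 against 141). The cut at Week 16 therefore looks deliberate, but it sits on the 7w label and not on the target day.

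**Step 4. Can the case arise?** The Week 14 dose of a Q2W subject falls on Day 7 × 14 + 1 = 99, so an early-termination visit within 14 days can fall as late as Day 113. The Week 15 dose of a QW subject falls on Day 7 × 15 + 1 = 106, so the visit can fall as late as Day 120. Day 113 is feasible in both schedules.

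**Step 5. What happens on Day 113.** The count maps to Week 24, although it was taken 169 − 113 = 56 days before the Week 24 target. Of the days in the ±3-day Week 16 visit window (110 to 116), Days 110 to 112 map to Week 16 and Days 113 to 116 to Week 24.

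**Step 6. Size per lost HiSCR75 responder (crude arm rate).** 1/55 = 1.82, 1/56 = 1.79, 1/57 = 1.75 and 1/58 = 1.72 percentage points. The denominators are the approximate 55 per comparison group in protocol 9.5, the 56 to 57 per izokibep group, and 2 × 28 to 2 × 29 = 56 to 58 for combined placebo.

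**The case against.** The strongest defence is that Day 112 is a deliberate cut. Day 113 is also the planned day of the first Period 2 dose, when placebo subjects switch to izokibep. A rule based on days alone cannot see whether a dose was given, so Day 112 is the last planned day wholly before the switch. That motive is plausible, but it does not justify the limit. SAP 5.1.3 places Week 16 assessments made before dosing in Period 1, and a no-Period-2-dose condition protects against the switch without discarding the target day.

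The objection on reach largely stands. Table 1 does not touch an attended Week 16 visit. Stopping study drug does not trigger it either, because protocol 7.1 encourages such subjects to stay and complete their assessments. A changed result needs study discontinuation, a visit recorded as early termination on that day, no Period 2 dose, a count that meets the criterion, and no antibiotic use that already forces non-response.

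It is also fair that the non-response does not come from this boundary alone. If protocol 9.3.1 governed, early-termination visits would not be mapped by day range at all, and the same subject would still be missing at Week 16. Protocol Section 9 describes itself as a summary, so Table 1 can be read as a narrow exception, but neither document says so. That conflict is a separate point.

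**Conclusion.** The Week 16 window in Table 1 is wrong by one day against SAP 5.1.1. The severity is minor. The documents give no expected number of affected subjects, and it may be zero. Each lost HiSCR75 responder moves the crude arm rate by about 1.7 to 1.8 points, narrowing the treatment difference if on izokibep and widening it if on placebo. The stratified estimate would move by a somewhat different amount. For AN count 0 to 2 the denominator is the Hurley Stage II subset, whose size the documents do not give. This rests on first dose being Day 1 for both SAP 5.1.1 and Table 1, as both state.

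A reader might infer more than the documents support:

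- *Week 16 visits held on Day 113 are generally lost.* They are not; they keep their nominal label.
- *The error biases the trial in one direction.* The direction depends on the affected subject's arm.
- *Days 114 to 116 are also misclassified, or the window should run to Day 140 by the midpoint pattern.* Only Day 113 follows from the day rule. The ±3-day allowance governs visit scheduling, and the cut at Week 16 departs from the midpoint pattern apparently on purpose.
- *Flare is also forced to non-response.* SAP 6.6.3.1 uses multiple imputation for missing counts in the main flare analysis, so the argument here does not extend to it.

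**What to change.** Before unblinding:

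1. In SAP Table 1, change the Week 16 window to Days 99 to 113 for early-termination visits with no Period 2 dose, and start Week 24 at Day 114. Any extension beyond Day 113, for example to Day 116 to match the ±3-day visit window, is an optional choice and not a correction; if it is made, state it at the same time.
2. Separately, state in SAP 5.1.4 that Table 1 is an exception for early-termination visits to protocol 9.3.1, or otherwise reconcile the two.

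The cost is two numbers, one condition and one sentence, with no new data. The documents do not say whether the primary analysis had been run when SAP version 3.0 was finalised. If treatment assignments are already known, report the number of early-termination visits on Day 113 by arm and show the corrected mapping as a sensitivity analysis, labelled post hoc.
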